2. REGISTRY OVERVIEW

2.1 Registry Design

The PROCLAIMSM Registry is a US-based, multicenter Registry designed to establish a high quality observational database of real-world clinical data on HD IL-2 when used to treat patients with mRCC, mM or other malignancies. The Registry will not, in any way, suggest changes in the treatment or management of the patients enrolled in the Registry. Therefore, physicians will continue to manage and treat patients according to standard of care and their own judgment.

The PROCLAIMSM Registry will start with a retrospective pilot data collection from a de-identified finite number of patient cases abstracted from their existing medical charts. The features collected will be identical to those planned for the prospective registry. The resulting database will be used to formulate hypotheses to be tested using the prospective registry database. Patients utilized in the retrospective analysis will be excluded from the prospective portion of the PROCLAIMSM Registry.

In the prospective portion of the Registry, sites will enroll patients who are expected to start a course of HD IL-2 therapy or have not yet completed their 1st course of HD IL-2

treatment. Once enrolled, the patient must receive at least one dose of HD IL-2 to remain in the Registry. Patients will be treated and followed according to the site's standard of care. This Registry will in no way induce changes in the management of individual patients. Clinical data features will be entered into an Electronic Data Capture (EDC) system, and organized into a registry database. The registry database will be interrogated according to database query protocols approved by the Steering Committee. (See **Appendix A** for an example data query proposal to the Registry Database). A subset of patients will participate in one of the Prometheus Proclivity studies (12PLK01, 12PLK02, 12PLK03). The Proclivity studies involve HD IL-2 in sequence with another therapy. Patients enrolled into any of the Proclivity studies and received a least one dose of HD IL-2 will be enrolled and followed in the Proclaim registry.

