4.5 Patient Inclusion/Exclusion Criteria

4.5.1 Inclusion Criteria

Patients who meet all of the following criteria will be eligible for inclusion into the Registry:

Prospective Cohort:

- 18 years of age and older
 - Given informed consent for participating in the Registry
- Is receiving or has received an initial course (2 cycles) of HD IL-2 and has not had post treatment imaging studies performed prior to enrollment. Data will only be collected and analyzed for patients who received at least one dose of HD IL-2. Exception: Patients enrolled in a Proclivity study (12PLK01, 12PLK02 or 12PLK03) can be enrolled into the registry at anytime.

Retrospective Cohort:

- 18 years of age and older
- Received HD IL-2 at the site prior to site initiation
- Have conformed to site specific guidelines permitting research on medical records without personal identification

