6. ANNUAL DATA OUTPUT SUMMARY

It is anticipated that a report will be generated on an annual basis in order to track the status of the registry database and have an executive summary on current use of IL-2 and outcomes. The following data will be included in the annual summary.

- Number of sites in the PROCLAIMSM Registry
- Number of patients enrolled (total, mM, and mRCC)
- Number of patients treated with HD IL-2 alone
- OS and PFS

- Investigator-determined ORR at 3-month assessment
- Number of dose per HD IL-2 treatment cycle
- Number of HD IL-2 cycles received per patient
- Causes of discontinuation of HD IL-2 treatment

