1. BACKGROUND

Proleukin[®] (the brand name of aldesleukin for injection), also commonly known as interleukin-2 (IL-2) or recombinant IL-2 (rIL-2), was approved by US FDA in early 1990s for treating adult patients with metastatic melanoma (mM) or metastatic Renal Cell Carcinoma (mRCC). Today high-dose IL-2 remains as an effective immunotherapy for fighting cancers and have been used alone as well as in conjunction with chemotherapy and other treatment options. It is an efficacious yet toxic therapy as it works through patient's profound immune system to trigger tumor response. Over the years, despite the high mortality and severe morbidity rates initially produced, HD IL-2 can now be safely and effectively administered by experienced clinicians. It is crucial to have and adhere to a standard dosing and patient assessment criteria during IL-2 administration in order to manage symptoms and minimize toxicities⁷.

In the studies leading to the approval of Proleukin, the complete and clinical overall response rates (CR and ORR) in treating mM and RCC were reported to be 5-6% and 15-28% respectively, median Overall Survival (OS) of HD IL-2 were reported at 16-19 months for mRCC but only 4.5-8.8 months for mM, and treatment-related death rates were reported as 2% and 4% for mM and RCC respectively^{8, 9, 10}. All those data all collected from patients studied prior to 1998.

2. HYPOTHESIS:

We hypothesize that patient mortality in contemporary clinical practice is significantly lower than the historical data reported in initial clinical trials in 1990s on patients with mM or mRCC treated with HD IL-2 therapy.

3. SPECIFIC AIMS:

- To estimate the cumulative treatment emergent mortality (TEM) observed in patients treated with HD IL-2 for mM or mRCC using prospective data from the PROCLAIMSM Registry database.
- To compare the TEM derived from the PROCLAIMSM Registry in mM patients treated with HD IL-2 with historical mortality data.
- To compare the TEM derived from the PROCLAIMSM Registry in mRCC patients treated with HD IL-2 with historical mortality data.
- To compare the TEM derived from the PROCLAIMSM Registry between mRCC and mM in patients treated with HD IL-2.

4. DESIGN AND PROCEDURE:

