The PROCLAIMSM Registry database will be the source of information to support all the data for fulfilling the query. One purpose of the registry database is to provide a research platform for researchers to study the real world treatment patterns and trends, as well as clinical outcomes, related to HD IL-2 therapy in patients with mRCC, mM or other malignancies in the United States. Treatment emergent mortality (TEM), which is defined as the incidence of patient death occurring from Day 1 of HD IL-2 administration until 2 weeks after the last dose of HD IL-2 with causality determined by the treatment physician, is standard data fields collected in the PROCLAIMSM Registry and will be the primary endpoint of this database query.

The primary endpoint will be analyzed for all patients and by stratifications for disease type (mM vs. mRCC). If a statistical difference is found in mortality rate comparison between this analysis dataset vs. historical data in Proleukin Prescription Information, analysis will be further stratified for metastatic sites, toxicity experience, line of treatment, and other ad hoc strata. The study outcomes will be compared to historical data as reported in the Prescription Information and literature, where such information exists.

The study will also examine incidence of treatment emergent death and overall survivals as time-dependent and patient-dependent variables and the cause of death between the two disease indications (mM vs. mRCC).

5. PATIENT POPULATION:

All prospective patients in the PROCLAIMSM Registry

6. ENDPOINTS:

The primary outcome is treatment emergent mortality (TEM). TEM is defined as the incidence of patient death occurring from Day 1 of HD IL-2 administration until 2 weeks after the last dose of HD IL-2 with causality determined by the treatment physician. The death event will be summarized by the cumulative incidence rate with disease types as stratification factors.

7. STRATIFYING FEATURES TO BE ANALYZED:

The TEM comparisons between data derived from the PROCLAIMSM Registry vs. historical data may be stratified for multiple tiers of analyses by the following features:

7.1 Patient related:

- Gender
- Age
- Weight and height
- Ethnicity
- Race
- ECOG score
- First Dose of HD IL-2 date

7.2 Disease related:

- Initial diagnosis date
- Disease type
- Metastasis
- Stage/remission status at enrollment
- Prior cancer therapies
- Surgery history
- Line of treatment with HD IL-2 (1st versus 2nd, 3rd ...)

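### The example query's population is wider than its mM/mRCC aims, and patients may enter after the mortality window has closed, which biases treatment-emergent mortality down and survival up within each disease

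*Protocol*

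**What the plan says.** **Population.** Appendix A, section 5, takes "All prospective patients in the PROCLAIMSM Registry". The registry accepts mRCC, mM or other malignancies (Protocol 2.1), and the inclusion criteria in 4.5.1 set no tumour type.

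**Aims.** The hypothesis concerns mortality "on patients with mM or mRCC treated with HD IL-2 therapy". The first aim is to estimate TEM "observed in patients treated with HD IL-2 for mM or mRCC using prospective data". The comparisons with history are written separately for each disease: "To compare the TEM derived from the PROCLAIMSM Registry in mM patients treated with HD IL-2 with historical mortality data" and "To compare the TEM derived from the PROCLAIMSM Registry in mRCC patients treated with HD IL-2 with historical mortality data". Appendix A, section 8.1, sizes each disease against its own historical rate, with a target of 1727 mM plus 345 mRCC, 2072 in total. Section 4 of the appendix nevertheless analyses the primary endpoint for all patients as well as by disease.

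**Entry.** Section 4.5.1 admits patients who are receiving or have received an initial course and have had no post-treatment imaging. It then adds: "Exception: Patients enrolled in a Proclivity study (12PLK01, 12PLK02 or 12PLK03) can be enrolled into the registry at anytime". Section 4.3 gives Proclivity patients the same freedom for consent. Of those studies, section 2.1 says: "The Proclivity studies involve HD IL-2 in sequence with another therapy".

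**Clocks.** TEM counts deaths from Day 1 of HD IL-2 to two weeks after the last dose (5.3 and Appendix A, section 6). OS and PFS start at HD IL-2 initiation (5.2).

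**The concern.** There are two separate defects.

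1. The population line and the aims do not describe the same patients. Someone who follows section 5 literally will include other malignancies in the all-patients primary analysis. The protocol quotes historical death rates only for mM (2%) and mRCC (4%), so that figure has nothing to be read against.

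2. Follow-up is counted from a date that can precede entry. Entry requires a living patient, or at least one for whom consent can still be obtained. A patient enrolled more than two weeks after the final HD IL-2 dose has survived the whole TEM window by construction, so adds one to the denominator and can add nothing to the numerator. A patient who enters mid-course has survived part of it. The same mechanism credits event-free time before entry to OS, and to PFS where entry presupposes no progression. Stratifying by disease does not help, because late entrants with mM or mRCC sit inside their own stratum.

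The direction matters. The hypothesis is that contemporary mortality is lower than the historical rate, and this bias lowers observed TEM. Proclivity patients also receive another therapy in sequence, and the query does not say whether they belong in the comparison.

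**Working it through.** **Step 1. Reproduce the planned numbers (Appendix A, 8.1).** Inputs: historical rates p0 of 2% (mM) and 4% (mRCC), expected rate p1 of 1%, 80% power, alpha 0.05, Fleiss method, 20% dropout. The figures come back as a one-sample, two-sided test with continuity correction:

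n = [(1.960·√(p0(1−p0)) + 0.842·√(p1(1−p1))) / (p0−p1)]²

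n_cc = (n/4)·[1 + √(1 + 2/(n·(p0−p1)))]²

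| Disease | p0 | p1 | n | n_cc | Stated | n_cc / 0.8 | Stated target |
|---|---|---|---|---|---|---|---|
| mM | 2% | 1% | 1282.6 | 1380.8 | 1381 | 1381/0.8 = 1726.25 | 1727 |
| mRCC | 4% | 1% | 243.2 | 275.5 | 276 | 276/0.8 = 345 | 345 |

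Each calculation tests one disease against its own fixed rate. Other malignancies carry no weight in it, so restricting the population to mM and mRCC changes no planned number.

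**Step 2. Effect of late entry on TEM.** Assume that a share q of a disease cohort enters after the window has closed and receives no further HD IL-2. The protocol gives no value for q, so a range is shown. Observed TEM is then p0·(1−q) even if nothing has improved.

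The test is taken as exact binomial with a nominal lower tail of 0.025. The rejection region is the largest number of deaths c with P(X ≤ c | n, p0) ≤ 0.025:
- mM, n=1381, p0=2%: c=17, actual level 0.020 (c=18 would give 0.034).
- mRCC, n=276, p0=4%: c=4, actual level 0.013 (c=5 would give 0.034).

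The chance of a false finding of lower mortality is P(X ≤ c | n, p0·(1−q)):

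| q | mM observed TEM | mM false finding | mRCC observed TEM | mRCC false finding |
|---|---|---|---|---|
| 0 | 2.0% | 0.020 | 4.0% | 0.013 |
| 5% | 1.9% | 0.036 | 3.8% | 0.020 |
| 10% | 1.8% | 0.062 | 3.6% | 0.028 |
| 20% | 1.6% | 0.162 | 3.2% | 0.058 |
| 30% | 1.4% | 0.349 | 2.8% | 0.113 |

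**Step 3. Effect on OS.** Assume exponential survival with a true median of 8.8 months (the upper mM figure in Protocol 1.1), so h = ln 2/8.8 = 0.0788 per month. Let a share f = 20% enter d months after first dose. Both f and d are assumptions. Counted from first dose without delayed entry, the apparent median t solves (1−f)·e^(−ht) + f·e^(−h(t−d)) = 0.5, which gives

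t = 8.8 + ln(1 − f + f·e^(hd))/h.

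- d=3: 8.8 + ln(0.8 + 0.2·1.267)/0.0788 = 9.5 months.
- d=6: 8.8 + ln(0.8 + 0.2·1.604)/0.0788 = 10.2 months.

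**The case against.** **The historical comparisons are already within disease.** This is correct. A reader might infer from the population line that other malignancies contaminate the mM and mRCC tests. They cannot: the second and third aims and section 8.1 are disease-specific, and a patient with another tumour falls in neither stratum. Other malignancies reach only the all-patients analysis.

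**Disease mix could create a spurious fall in a pooled rate.** The arithmetic is easy. Weighting 2% and 4% by the 270 and 255 patients in the cited cohorts gives (5.4+10.2)/525 = 2.97%. The planned mix gives (34.54+13.8)/2072 = 2.33%, an apparent 21% reduction with no improvement. However, the plan states no pooled historical rate, names no pooled comparison among its aims and powers none. The figure describes a test that is not in the document.

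**Section 6 lists OS, PFS and ORR without a disease split.** It is a descriptive annual list, and table layout is reasonably settled elsewhere. It also calls separately for the "Number of patients treated with HD IL-2 alone". This is not pressed.

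**Sections 2.1 and 4.3 expect ordinary patients to enrol or consent before the first course is complete.** This has weight, since it would limit late entry outside Proclivity. But 4.5.1 admits patients who have already received the initial course, with imaging as the only cut-off, and the initial tumour assessment is usually about three months after the start (4.7.2). The sections do not agree. Even under 4.3 a patient may enter after some doses, having survived part of the window. Section 4.3 itself exempts Proclivity patients.

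**Including patients who receive another therapy may be legitimate** in a study of contemporary practice. This stands in part: it argues for showing Proclivity patients separately, not necessarily for discarding them. Other interval therapy is only an optional stratifier in Appendix A, section 7.

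**Appendix A is an example query**, with analyses set case by case and a data extract plan to follow. That lowers the weight. It does not remove the contradiction, since the example has its own proposal number, sample size and single planned significance assessment.

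**Conclusion.** The point holds in two parts.

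- The population line contradicts the query's title, aims and sample size. The consequence is limited to an all-patients TEM figure without a benchmark.
- The entry rules, combined with clocks that start at first dose, allow survivor bias within the mM and mRCC strata. TEM is pushed down, in favour of the hypothesis, and OS and PFS are pushed up.

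The direction of the second part follows from the text, but its size does not. The protocol gives no share of Proclivity or late-entering patients, no entry times and no tumour types for the Proclivity studies. The error rates above therefore assume a late-entry share, zero TEM in late entrants and an unchanged true rate. On those assumptions a 10% share roughly triples the mM false-finding rate (0.020 to 0.062), and the effect in mRCC is smaller. The OS shift from 8.8 to 9.5 or 10.2 months rests on an assumed share, an assumed delay and exponential survival.

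A reader might also infer that registry patients are in fact selected on outcome, or that removing Proclivity patients would cure the problem. The documents support neither. Section 2.1 says dosed Proclivity patients will be enrolled, so late selective entry is permitted but not shown to occur. Section 4.5.1 leaves the same opening for other patients.

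**What to change.** 1. In Appendix A, section 5, define the population as prospective mM and mRCC patients. Keep tests against historical rates within disease, and report other malignancies descriptively if wanted.
2. For TEM, restrict the primary set to patients enrolled at or before their first HD IL-2 dose, or estimate cumulative incidence with delayed entry at the enrolment date. Apply the rule to every patient, not only Proclivity patients.
3. For OS and PFS, keep first dose as time zero but let each patient enter the risk set at enrolment.
4. Report Proclivity patients separately or as a sensitivity analysis, and state which.
5. Reconcile sections 2.1, 4.3 and 4.5.1 on the latest enrolment point for patients outside Proclivity.

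**Cost.** This is mainly wording, using disease type, enrolment date and dosing dates that the registry should already hold. The required numbers stay at 1381 and 276. The drawback is a smaller primary TEM set. How much smaller depends on how many patients enrol after their first dose, which the protocol does not say. If that is common, the delayed-entry option keeps more of the data.

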8. STATISTICAL CONSIDERATIONS

8.1 Determination of Sample Size

The sample size for this analysis is determined based on anticipated differences between data from the PROCLAIMSM Registry and historical data on the death rate observed in patients with mM or mRCC treated with HD IL-2. The death rates of 2% and 4% were reported in the historical data for mM and mRCC respectively but are expected to be no more than 1% for either disease. The methods of Fleiss are used to determine the sample size necessary to detect differences in death rate between data from the PROCLAIMSM Registry and historical data. The number of patients necessary to detect 2% and 3% difference in death rate between PROCLAIM and historical data with 80% power at $\alpha=0.05$ significance level is 1381 and 276 for patients with mM and mRCC respectively. To allow for a 20% dropout rate, a target sample size of N=1727 patients with mM and N=345 patients with mRCC is chosen for a total of N=2072 patients.

8.2 Statistical Analyses

Statistical analysis will be generated on a specific case by case basis.

8.3 Interim Analyses

Data will be requested and analyzed periodically and descriptively throughout the life cycle of the PROCLAIMSM Registry. Statistical significance of the difference in death rate between data from the PROCLAIMSM Registry and historical data will be summarized once and after the dataset reach the sample size requirements as specified in Section 8.1. After this analysis protocol is approved by the Registry Steering Committee, a data extract plan will be prepared and the data to conduct the necessary analyses will be extracted from the registry database into a query-specific research dataset with controlled assessment.

--- End of the Example Registry Database Query ---

